	progression) by telephone contact or other method every 3 months (\pm 1 week) for until study closure.	progression) by telephone contact or other method every 12 weeks \pm 28 days for until study closure.	
Section: Appendix B Schedule of Disease Assessments, footnote g, sentence 1	Replace: Bone marrow samples: Bone marrow biopsy or aspirate slides will be obtained to confirm sCR or CR, or as clinically indicated.	With: Bone marrow samples: Bone marrow biopsy or bone marrow aspirate will be obtained to confirm sCR or CR, or as clinically indicated.	Revised text for consistency within overall protocol
Section: Appendix D Schedule of Study Assessments for the Pharmacokinetic Sparse Sampling and Intensive Pharmacokinetic & Pharmacokinetic Pharmacodynamic Sub-Study		Add: ^a 24 hours \pm 2 hours after the end of the Day 15 infusion ^b 48 hours \pm 2 hours after the end of the Day 15 infusion ^c 168 hours \pm 2 hours after the end of the Day 15 infusion ^d 24 hours \pm 2 hours after the end of the Day 16 infusion ^e 144 hours \pm 2 hours after the end of the Day 16 infusion	Added text to clarify timing of PD sampling
Section: Appendix G Summary of International Myeloma Working Group Uniform Response Criteria (IMWG-URC), sCR, bullet 3	Replace: Absence of clonal cells in bone marrow ^c by immunohistochemistry or immunofluorescence ^c	With: Absence of clonal cells in bone marrow by immunohistochemistry or immunofluorescence ^c	Administrative change
Section: Appendix G Summary of International Myeloma Working Group Uniform Response Criteria (IMWG-URC), CR	Replace: CR ^b	Add: CR ^{b, h}	Added footnote h to clarify that for patients with sFLC measurable disease only, normal sFLC ratio is also required for CR in addition to the CR criteria listed in the

Section	Text in Protocol	Amended Text	Rationale for Change
			table.
Section: Appendix G Summary of International Myeloma Working Group Uniform Response Criteria (IMWG-URC), CR, bullet 3	
Replace:
 
 • < 5% plasma cells in bone marrow^c 	
With:
 
 • < 5% plasma cells in bone marrow 	Footnote c is not applicable to this criterion.
Section: Appendix G Summary of International Myeloma Working Group Uniform Response Criteria (IMWG-URC), Stable disease	
Replace:
 
 • Not meeting criteria for CR, VGPR, PR, or PD 	
With:
 
Not meeting criteria for sCR, CR, VGPR, PR, MR, or PD
	Added sCR and MR for completeness.
Section: Appendix G Summary of International Myeloma Working Group Uniform Response Criteria (IMWG-URC), footnote	
Replace:
 
Note: Patients with measurable disease in both serum (SPEP) and urine (UPEP) at study entry are required to meet response criteria in both UPEP and SPEP in order to qualify for a MR or better. Conversely, it should be noted criteria for PD only needs to be met, and confirmed, in 1 parameter. For patients without measurable protein on UPEP at baseline, UPEP will need to be repeated to confirm a response.
	
With:
 
Note: For patients without measurable protein on UPEP at baseline, UPEP will need to be repeated to confirm a response of VGPR or better.
	
Removed the sentences ‘Patients with measurable disease in both serum (SPEP) and urine (UPEP) at study entry are required to meet response criteria in both UPEP and SPEP in order to qualify for a MR or better. Conversely, it should be noted criteria for PD only needs to be met, and confirmed, in 1 parameter. ‘ since they are redundant to footnote a.
 
Added ‘of VGPR or better’ to clarify UPEP will need to be repeated to confirm VGPR or better (not

Section	Text in Protocol	Amended Text	Rationale for Change
			needed for PR or MR) when UPEP is not measurable at baseline.
Section: Appendix G Summary of International Myeloma Working Group Uniform Response Criteria (IMWG-URC), footnote g	Replace: The plasmacytoma specifications for PD are based on Onyx’s interpretation of the IMWG-URC and practical considerations for study execution.	With: The plasmacytoma specifications for PD are based on the Sponsor’s interpretation of the IMWG-URC and practical considerations for study execution.	Administrative change
Section: Appendix G Summary of International Myeloma Working Group Uniform Response Criteria (IMWG-URC), footnote h		Add: In patients with sFLC measurable disease only, normal sFLC ratio is required for CR.	To clarify that for patients with sFLC measurable disease only, normal sFLC ratio is also required for CR in addition to the CR criteria listed in the table.
Section: Appendix J Patient Reported Outcomes, paragraph 1, sentence 1	CCI		Revised text for clarification
Section: Appendix K Country Specific Pregnancy And Contraceptive Supplement, pregnancy prevention information, female subjects, paragraph 2	Replace: WOCBP must use a highly effective method of birth control during treatment and for an additional 30 days after the last dose of protocol-required therapies. Highly effective methods of birth control include: 
• Combined (estrogen and progestogen	With: WOCBP must use a highly effective method of birth control during treatment and for an additional 30 days after the last dose of protocol-required therapies. Highly effective methods of birth control for female participants or their male partner include:	Updated text to align with current carfilzomib core safety language

Section	Text in Protocol	Amended Text	Rationale for Change
	
containing) hormonal contraception associated with inhibition of ovulation
 
 ○ Oral ○ Intravaginal ○ Transdermal 
 ● Progestogen-only hormonal contraception associated with inhibition of ovulation 
 ○ Oral ○ Injectable ○ Implantable ● Intrauterine device (IUD) ● Intrauterine hormonal-releasing system (IUS) ● Bilateral tubal occlusion 	
 ● Combined (estrogen and progestogen) hormonal methods: pills, vaginal ring, or skin patch. ● Single hormonal methods (progestogen to stop the release of the egg from the ovary): pills, shots/injections, implants (placed under the skin by a healthcare provider) ● Intrauterine device (IUD) ● Intrauterine hormonal-releasing system (IUS) surgery to tie both fallopian tubes (bilateral tubal ligation/occlusion) 	

Section: Appendix K Country Specific Pregnancy And Contraceptive Supplement, Male Subjects, paragraph 1
	
Replace: Male subjects whose partner is a WOCBP potential must use an acceptable method of effective birth control during treatment and for an additional 30 days after the last dose of protocol-required therapies.
 
 ● Acceptable methods of birth control for male subjects include: ● The female partner uses a: 
 ○ Hormonal birth control method 
 – Oral – Injectable – Transdermal – Implantable – Intravaginal ○ Intrauterine device (IUD) 	
With: If the male subjects sole female partner has received medical confirmation that she is postmenopausal or she has had a permanent sterilization method (hysterectomy, bilateral oophorectomy, or bilateral salpingectomy) or the male subject has had a vasectomy with medical confirmation of surgical success, or his sole female partner has had a bilateral tubal ligation/occlusion, additional contraceptive methods are not required during this study. Otherwise, if the male subject’s female partner could become pregnant, the male must:
 
 ● Practice true sexual abstinence. (Refraining from heterosexual intercourse during treatment and for an additional 90 days) 	
Updated the window for breastfeeding following the last dose of drug administration.

Section	Text in Protocol	Amended Text	Rationale for Change
	
 ○ Intrauterine hormonal-releasing system (IUS) ○ The female partner has had a bilateral tubal occlusion • The male subject has had a vasectomy and has received a medical assessment of the surgical success. • Two barrier methods: One by each partner and at least one of the barrier methods must include spermicide 
 ○ Male must use a condom ○ Female partner may use a diaphragm, cervical cap, or contraceptive sponge. (Note: The female condom cannot be used with a male condom). • Sexual abstinence: Refraining from heterosexual intercourse during the entire period of risk associated with the study treatment. The reliability of sexual abstinence needs to be evaluated in relation to the duration of the clinical trial and the preferred and usual lifestyle of the subject. 
Unacceptable birth control methods for female and male subjects during treatment with protocol-required therapies include:
 
 • Periodic abstinence (e.g., calendar, ovulation, symptothermal, post-ovulation methods) • Withdrawal (coitus interruptus) • Spermicides only • Lactational amenorrhoea method (LAM) 
Female condom and male condom should not be
	
following the last dose of study drug administration. The reliability of sexual abstinence needs to be evaluated in relation to the duration of the clinical trial and be the preferred and usual lifestyle of the subject.)
 
Or
 
 • Use a condom with spermicide during treatment and for an additional 90 days following the last dose of study drug administration. (Note a condom without spermicide is acceptable in countries where spermicide is not commercially available.) 
The female partner should also consider using an acceptable method of effective contraception such as:
 
 • Intrauterine device (IUD) • Intrauterine hormonal-releasing system (IUS) • Hormonal birth control method: pill, shots/injections, implants (placed under the skin by a healthcare provider), skin patches, or a vaginal ring • Female barrier method: diaphragm, cervical cap, or contraceptive sponge (a female condom is not an option because there is a risk of tearing when both partners use a condom) 
 • Male subjects must not donate sperm during treatment and for an additional 90 days following the last dose of study drug administration. 	

Section	Text in Protocol	Amended Text	Rationale for Change
	used together	Males with pregnant partners must practice true sexual abstinence or wear a condom during vaginal sex to prevent exposure to the embryo/fetus through semen.	
Section: Appendix L Summary of Changes		Add: Updated Appendix L to include current summary of changes.	Administrative change

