Health related Quality of Life (HRQL):	
The following patient reported outcomes (PRO) will be collected in the study:
 
 • The EORTC 30-item QLQ-C30 questionnaire • The EORTC 20-item QLQ-MY20 module specifically designed to address the quality of life for those with multiple myeloma • The EQ-5D-5L and patient reported convenience and satisfaction questionnaire 
QLQ-C30, QLQ-MY20, and EQ-5D-5L questionnaires should be administered prior to study treatment on Day 1 of Cycle 1, then every second cycle (Cycle 1, 3, 5, etc) during treatment and every 12 weeks (every 84 days \pm 4 days) until progression, or withdrawal of consent during LTFU. Patient convenience and satisfaction questionnaire will be collected at Day 1 Cycle 2 and end of treatment (EOT) only. Healthcare resource utilization will be collected for all subjects during the study. Details on hospitalizations (not related to adverse events) will also be collected.

Safety variables:	Safety and tolerability will be assessed by incidence and severity of adverse events and changes from baseline of all relevant parameters, including laboratory values, physical examination, vital signs, and electrocardiogram (ECG). Severity of adverse events will be assessed according to the National Cancer Institute-Common Terminology Criteria for Adverse Events (NCI-CTCAE), Version 4.03. All subjects will be monitored for adverse events for at least 30 days after the last administration of study treatment.

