7 SUBJECT RANDOMIZATION

The primary investigator will determine the subject's eligibility, ensuring that the results of the required screening procedures are consistent with all of the eligibility criteria presented in [Section 5](#). No eligibility waivers will be permitted. Randomization will be carried out centrally through an interactive voice and web response (IVR/IWR) system. Please refer to the separate study reference manual.

Eligible subjects will be randomized in a 1:1 ratio to either:

- Arm A: Once-weekly carfilzomib with dexamethasone regimen
- Arm B: Twice-weekly carfilzomib with dexamethasone regimen

The randomization will be stratified by the following factors:

- International Staging System (ISS) at study entry (Stage 1 versus Stage 2 or 3) ([Appendix H](#))
- Refractory to bortezomib treatment (Yes versus No)
- Age (< 65 versus ≥ 65 years)

Within each stratum defined by the stratification factors, subjects will be randomized according to a randomly permuted blocked randomization scheme.

Study treatment will ideally commence on the day of randomization, but at least within 5 calendar days of randomization. Initiation of study treatment (Cycle 1 Day 1) > 5 calendar days after randomization must be approved by the study medical monitor.

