10.7 PATIENT REPORTED OUTCOMES

Patient reported outcomes (PRO) are based on the following questionnaires (refer to Appendix J).

All questionnaires should be collected on Day 1 of Cycle 1, then every second cycle (Cycle 1, 3, 5, etc) during treatment. The questionnaires listed below should be completed by the subject prior to drug administration during treatment cycles:

- EORTC QLQ-C30
- EORTC QLQ-MY20
- EQ-5D-5L
- Patient reported convenience and satisfaction (collected Day 1 Cycle 2 and EOT only)

Health-related Quality of Life (HRQL) will be assessed by the EORTC 30-item QLQ-C30 questionnaire and by the 20-item QLQ-MY20 module specifically designed to address the quality of life for those with multiple myeloma ([Aaronson 1993](#); [Fayers 2001](#); [Cocks 2007](#)). The primary constructed scales from the QLC-C30 are:

- Global Health Status/Quality of Life
- Physical functioning
- Role functioning
- Emotional functioning
- Cognitive functioning
- Social functioning
- Nine additional scales can be derived:
- Fatigue

- Nausea and vomiting
- Pain
- Dyspnea
- Insomnia
- Appetite loss
- Constipation
- Diarrhea
- Financial difficulties

The primary scales from the QLQ-MY20 include disease symptoms, side effects of treatment, body image and future perspectives.

The EQ-5D-5L is a standardized measure of health status developed by the EuroQol Group in order to provide a simple, generic measure of health for clinical and economic appraisal ([EuroQol Group 1990](#)). The EQ-5D-5L version will be used in this study. The EQ-5D-5L consists of a 1-page descriptive system and a 1-page EQ Visual Analogue scale (EQ VAS). The descriptive system comprises 5 dimensions (mobility, self-care, usual activities, pain/discomfort, and anxiety/depression). Each dimension is then scored on 5 levels: no problems, slight problems, moderate problems, severe problems, and extreme problems. The respondent is asked to indicate his/her health state by ticking (or placing a cross) in the box against the most appropriate statement in each of the 5 dimensions. The EQ VAS records the respondent's self-rated health on a 20 cm vertical, visual analogue scale with endpoints labelled 'the best health you can imagine' and 'the worst health you can imagine'. This information can be used as a quantitative measure of health as judged by the individual respondents.

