Synopsis: Synopsis, Exclusion Criteria, criterion 226, 5.2 Exclusion Criteria, criterion 226		Delete: 226. Female subjects who are pregnant or lactating	Removed text to avoid duplication with the inclusion criteria
Section: Synopsis, Efficacy Variable, paragraph 3	Replace: Disease assessments according to the International Myeloma Working Group-Uniform Response Criteria (IMWG-URC) will be conducted at baseline and then at Cycle 2 Day 1 (C2D1) and on Day 1 of every cycle thereafter until progression.	With: Disease assessments according to the International Myeloma Working Group-Uniform Response Criteria (IMWG-URC) will be conducted at baseline and then every 28 days (± 4 days) thereafter until progression.	Updated text for disease assessment timepoints to align with other sections in protocol
Section: Synopsis, Intensive PK and PDn Substudy	Replace: Intensive pharmacokinetic (PK) and pharmacodynamic (PDn) samples will be obtained as a substudy (approximately n = 15 in each arm) from subjects who consent to the additional testing at selected sites. Pharmacokinetic samples will be collected on Day 15 of Cycle 1 and PDn	With: Intensive pharmacokinetic (PK) and pharmacodynamic (PDn) samples will be obtained as a substudy (approximately n = 15 evaluable subjects in each arm) from subjects who consent to the additional testing at selected sites. Pharmacokinetic samples will be collected on Day 15 of Cycle 1 and PDn samples will be collected	Revised text for consistency within overall protocol

Section	Text in Protocol	Amended Text	Rationale for Change
	samples will be collected on Days 1, 15, 16, 17, and 22 of Cycle 1.	on Days 1, 15, 16, 17, and 22 of Cycle 1.	
Section: Synopsis, Health related Quality of Life (HRQL), paragraph 2, sentence 1	Replace: All questionnaires should be administered prior to study treatment on Day 1 of Cycle 1, then every other cycle during treatment and every 12 weeks (every 84 days ± 4 days) until progression, or withdrawal of consent during LTFU.	With: QLQ-C30, QLQ-MY20 and EQ-5D-5L questionnaires should be administered prior to study treatment on Day 1 of Cycle 1, then every second cycle (Cycle 1, 3, 5, etc) during treatment and every 12 weeks (every 84 days ± 4 days) until progression, or withdrawal of consent during LTFU.	Revised text for clarification

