4.2 Planned Covariates

The primary analysis of PFS, ORR and OS will be stratified by the stratification factors at randomization: ISS stage at study entry (Stage 1 versus Stage 2 or 3), refractory to bortezomib treatment (yes versus no), and age ($< 65 \text{ versus} \ge 65 \text{ years}$).

5. Hypotheses and/or Estimations

The inferential comparison of PFS between treatment groups will be made using a log-rank test stratified by randomization stratification variables. The 1-sided p-value from the stratified log-rank test will be compared against the value specified by the alpha spending function specified in Section 8 at the given analysis (interim or final) to test the null hypothesis that weekly arm doesn't have superior PFS than twice weekly arm. The inferential comparison of ORR between treatment groups will be made using a Cochran-Mantel-Haenszel test stratified by randomization stratification variables. The inferential comparison of OS between treatment groups will be made using a log-rank test stratified by randomization stratification variables.

6. Definitions

Anti-myeloma therapies during long term follow-up

Anti-myeloma therapies during long term follow-up will be those therapies entered in the anti-myeloma therapy case report form (CRF) administered during the long term follow-up period of the study.

Baseline

For analyzing progression-free survival time (PFS) and overall survival time (OS), baseline will be defined as the day of randomization.

For the analysis of other endpoints, baseline will be defined as the value measured on day1 of the first cycle of protocol-specified therapy. The protocol specifies that all study procedures on day 1 should be completed before the initiation of protocol-specified therapy, which will be the assumption in the analysis, unless the time of the assessment is recorded. If a day 1 value is not available, the latest value before the day of the start of protocol-specified therapy will be used. If a subject doesn't receive any protocol-specified therapy, then the latest value prior to or on randomization date will be used.

Best overall response

Statistical Analysis Plan: 20140355

Date: 09 Jun 2017 Page 12

Best overall response will be assessed by computational assessment, Independent Review Committee (IRC) and investigator. The primary analysis of ORR will be based on best overall response assessed by computational assessment.

Best overall response by computational assessment

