10.5.3 Exploratory Efficacy Analysis

The KM summaries described in Section 10.1 will be performed by treatment group for duration of response and clinical benefit.

Time to response will be summarized by the non-missing sample size (n), mean, standard deviation, median, minimum, and maximum for responders by treatment group.

QLQ-C30, QLQ-MY20 and EQ-5D-5L questionnaires will be administered prior to study treatment on Day 1 of Cycle 1, then every second cycle (Cycle 1, 3, 5, etc) during treatment and every 12 weeks (every 84 days ± 4 days) until progression, or withdrawal of consent during LTFU. Patient convenience and satisfaction questionnaire will be collected at Cycle 2 and EOT only. All QLQ-C30 and QLQ-MY20 subscale scores will

Statistical Analysis Plan: 20140355

Date: 09 Jun 2017 Page 31

be summarized descriptively by visit and by treatment group using the number of subjects with non-missing data (n), mean, standard deviation, median, minimum and maximum. Change from baseline will be summarized using the same statistics. EQ-5D-5L data will be summarized by presenting the frequency and proportion of each level for each dimension by visit and by treatment group. EQ VAS data arm will be summarized using the same method for QLQ-C30 and QLQ-MY20 subscale scores. Patient convenience and satisfaction questionnaire has only two questions about whether the patients feel the carfilzomib dosing schedule convenient and how statisfied/dissatisfied they are with the dosing schedule. The frequency and proportion of each category will be summarized for the two questions by treatment group at cycle 2 and EOT. The comparison analyses of health-related quality of life between treatment groups will be implemented in addition to the descriptive analyses described above. For instance, Global Health Status/QoL scale, an important subscale of QLQ-C30, will be compared between treatment groups across visits using a restricted maximum likelihood-based mixed model for repeated measures (MMRM) under the assumption of missing at random (MAR) (Mallinckrodt et al, 2008).

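### The first quality-of-life questionnaire is scheduled on Cycle 1 Day 1 with no requirement to precede open-label randomization, so exploratory change-from-baseline results can be biased by reaction to allocation

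*Protocol*

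**What the plan says.** **When the form is first given.** The Amendment 3 entry in Protocol Appendix O records the wording as "QLQ-C30, QLQ-MY20 and EQ-5D-5L questionnaires should be administered prior to study treatment on Day 1 of Cycle 1". The current Synopsis, under Health related Quality of Life, keeps it with one comma added and says of the QLQ-C30, QLQ-MY20 and EQ-5D-5L: "questionnaires should be administered prior to study treatment on Day 1 of Cycle 1, then every second cycle". Protocol Section 10.7 has the same content in other words: "All questionnaires should be collected on Day 1 of Cycle 1, then every second cycle". It adds that the forms come before drug administration during treatment cycles. In the Appendix A schedule the questionnaire row is marked at Day 1, end of treatment and long-term follow-up; the Screening and Baseline cells are empty. Footnote g and SAP Section 10.5.3 repeat Cycle 1 Day 1.

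**When that is relative to randomization.** Protocol Section 7 says: "Study treatment will ideally commence on the day of randomization, but at least within 5 calendar days of randomization". A longer gap needs medical monitor approval. Section 4.1 describes the trial as open-label.

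**How the value is used.** SAP Section 6 (Definitions, Baseline) takes the randomization day as baseline for PFS and OS. For all other endpoints, "baseline will be defined as the value measured on day1 of the first cycle". SAP Section 10.5.3 summarizes the QLQ-C30 and QLQ-MY20 subscales by visit and arm and continues: "Change from baseline will be summarized using the same statistics". EQ VAS is handled the same way. The section also plans comparisons between arms and gives one example, a mixed model for repeated measures (MMRM) of Global Health Status. It does not say whether the response is the raw score or the change, or whether baseline is a covariate.

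**The concern.** A baseline is safe to subtract or adjust for because allocation cannot have influenced it. Here the only ordering rule is that the form precedes dosing; no rule places it before randomization or before the subject knows the arm.

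The arms differ in schedule: three carfilzomib infusion days per cycle against six. Convenience is part of the study rationale in Protocol Section 2.4. A subject who has just learned which schedule awaits may rate global health, emotional functioning or future perspective differently for that reason alone. If the reaction differs between arms, it enters the baseline and from there every change score built on it, with no effect of the drug regimen.

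At stake is the reading of the exploratory patient-reported comparison of the two schedules.

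**Working it through.** **Inputs from the documents**
- First questionnaire: Cycle 1 Day 1, pre-dose (Synopsis; Protocol 10.7; Appendix A and footnote g; SAP 10.5.3).
- Gap from randomization: 0 to 5 calendar days, longer with approval (Protocol 7).
- Open-label (Protocol 4.1).
- Baseline for these endpoints: the Cycle 1 Day 1 value (SAP 6).
- Analysis set: all randomized subjects (SAP 7.4).

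The plan states no power, standard deviation, correlation or effect size for the questionnaires, so there is no figure of its own to reproduce. The 83% power for PFS plays no part.

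**Who is exposed**
- Start on a later day than randomization: the form is necessarily completed after randomization.
- Start on the same day: the order of form and randomization is not specified, so it may be either.
- Randomized but never treated: SAP Section 6 falls back to the latest value on or before the randomization date, yet no questionnaire is scheduled then. These subjects are in the analysis set with no scheduled baseline.

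**How a baseline shift carries through**

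Let d be the between-arm shift at the first form caused by knowing the allocation, k the share still present at a later visit, and b the slope of the later score on baseline. Assume no true effect.
- Change score: later shift minus baseline shift = kd - d = (k-1)d.
- Baseline as covariate: later shift minus b times baseline shift = kd - bd = (k-b)d.
- Raw later score, no baseline: kd.

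With b = 0.5, in points on the 0 to 100 scale:

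| d | k | change | adjusted | raw |
|---|---|---|---|---|
| 2 | 0 | -2 | -1 | 0 |
| 2 | 0.5 | -1 | 0 | 1 |
| 2 | 1 | 0 | 1 | 2 |
| 5 | 0 | -5 | -2.5 | 0 |
| 5 | 0.5 | -2.5 | 0 | 2.5 |
| 5 | 1 | 0 | 2.5 | 5 |

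A simulation of 200,000 subjects with d = 2, k = 0 and b = 0.5 gave -1.91 for change and -0.92 adjusted, against -2 and -1 by formula.

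**Illustrative rejection rates**

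Everything here is assumed: 195 subjects per arm with a later score, SD 20 to 24, correlation r of 0.5 to 0.6 (with b = r), and a two-sided 5% test, which the SAP does not specify.
- SE(change) = SD × √(2(1-r)) × √(2/195)
- SE(adjusted) = SD × √(1-r²) × √(2/195)
- Rejection = P(|Z + bias/SE| > 1.96)

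| k | d | change score, % | baseline-adjusted, % |
|---|---|---|---|
| 0 | 2 | 13.0–19.7 | 7.6–11.5 |
| 0 | 3 | 23.5–38.1 | 11.0–19.9 |
| 0 | 5 | 53.9–78.8 | 22.1–45.7 |
| 0.5 | 2 | 7.0–8.6 | 5.0–5.2 |
| 0.5 | 3 | 9.5–13.1 | 5.0–5.4 |
| 0.5 | 5 | 17.7–28.1 | 5.0–6.1 |
| 1 | 2 | 5.0 | 7.0–8.8 |
| 1 | 3 | 5.0 | 9.5–13.7 |
| 1 | 5 | 5.0 | 17.7–29.7 |

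The result depends heavily on k. The change score does worst when the reaction fades; the adjusted model errs in opposite directions at k = 0 and k = 1.

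**The case against.** Four objections deserve an answer.

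**Knowledge of the arm is not universal.** A reader might infer that every subject answers the first form already knowing the arm. The documents do not support that. Treatment ideally starts on the day of randomization, and on that day the form could come first. This stands; the point is limited to what the plan permits.

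**The reaction may last.** The schedule that provokes it continues, so full fading is not the obvious case, and a fully persistent shift cancels from the change score. With a pre-randomization baseline a persisting reaction would enter the change score as kd, which is larger in size than (k-1)d whenever k exceeds 0.5. The arithmetic is right. But the cancellation is accidental, depends on an unknown k, and does not carry over to the adjusted model. What persists is a feature of open-label reporting that no timing of the baseline removes. Only a pre-randomization form gives a baseline that allocation cannot affect.

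**The tests are not the SAP's.** Change from baseline is summarized descriptively, and the form of the MMRM is not stated. An MMRM on raw later scores without baseline would carry nothing from the baseline shift. This stands: the rejection rates illustrate sensitivity and are not operating characteristics of this trial.

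**The reach is narrow.** EQ-5D-5L dimensions are reported as frequencies by visit. The convenience and satisfaction item, which asks about the schedule directly, is collected at Cycle 2 and end of treatment and has no baseline. All of these results are exploratory. This also stands.

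**Conclusion.** The concern holds in limited form. Followed exactly, the plan gives a patient-reported baseline that is post-randomization for later starters and may be so for same-day starters, and no safeguard or sensitivity analysis addresses this.

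The affected results are change from baseline in the QLQ-C30 and QLQ-MY20 subscales and EQ VAS, and the Global Health Status MMRM if it uses change or a baseline term. The bias is (k-1)d or (k-b)d. The documents give no basis for d, k or b, so neither size nor direction can be stated.

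It would be wrong to read this as a threat to the trial's main conclusions. PFS, ORR and OS do not use this baseline, and the questionnaires lie outside the testing hierarchy. The EQ-5D-5L dimension frequencies and the convenience and satisfaction item are also unaffected. Severity is low to moderate; the case for acting rests on how little the remedy costs.

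**What to change.** **Protocol** (Synopsis, Section 10.7, Appendix A and footnote g): require the first QLQ-C30, QLQ-MY20 and EQ-5D-5L after eligibility is confirmed and before the IVR/IWR randomization call.

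**SAP Section 6:** define the patient-reported baseline as the last questionnaire completed before randomization. This also gives randomized but untreated subjects a scheduled baseline.

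**SAP Section 10.5.3:** state the MMRM response and whether baseline is a term in the model.

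**Subjects already enrolled without a pre-randomization form:** flag the Cycle 1 Day 1 value as post-randomization, compare it between arms, and add a sensitivity analysis on raw post-baseline scores. That analysis avoids the baseline shift but not a reaction that persists.

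**Cost:** a reordering of steps, often within a single visit, and a few sentences across the two documents. Sample size and power do not change. Occasionally a subject will complete the forms and then not be randomized.
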